4.2 Study Outcome Measures

4.2.1 Primary Outcome Measures

The primary outcome is the correlation in estimated BAL as measured by the breathalyzer and the wristwatch sensor during the second alcohol self-administration trial. BAL and wristwatch sensor data correlation will be analyzed by repeated measures correlation (rmcorr) analysis, as described in more detail in section 12.

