12.1 Study Hypotheses and Planned Analyses

Calibration Phase I

The objective of the Phase 1 of this study is to use data obtained from subjects who have consumed alcohol in a controlled laboratory setting to develop a model of the relationship between BrAc and TAC measurements that will allow for the determination of estimated blood alcohol levels (BAL) from TAC data collected over extended periods of time.

The results of several studies support the expectation that for most subjects the time to reach peaked alcohol concentrations (Tmax) will be greater for TAC as compared BrAc values [20-21]. In contrast, maximal BrAc concentration (Cmax) values are expected to be smaller be for TAC values collected during test session as compared to those obtained for BrAC measurements. Nevertheless, if TAC values detected by the test device are directly related to blood alcohol levels there should be a strong correlation between the CMax for both TAC and BrAc measurements. Therefore, we hypothesize that for correlations between Cmax values for TAC and BrAc values should be have an r value of 0.8 or greater. A finding consistent with this hypothesis will provide evidence that the test alcohol monitor is able to detect TAC levels that are directly related to BAL.

Validation Phase

Validation Phase

TAC data collected during validation phase will be converted into predicted BAL values for individual subjects using the models developed in the Phase 1 of this investigation. Data obtained during the validation phase will be inspected to determine if there are differences in the sensitivity between the breathalyzer and the wristwatch sensor. Time concentration curves for BrAc and predicted BAL values will be produced for each subject. These curves will be examined to check whether there are any systematic differences between these two measures in the time needed to reach maximal concentration levels for each of the subjects (Tmax) and between the values obtained at the maximum concentration levels (Cmax).

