Predicted BAL that will be determined from TAC data are expected to be equivalent to BrAc concentrations. We, therefore hypothesize that there will be a strong correlation between BAL and BrAc measurements obtained at the same time points for the individual subjects. The reference breathalyzer response is known to be linear over the range of expected blood alcohol levels in the study [23]. Therefore, the breathalyzer and predicted BAL values are expected to be linearly related to each other. To confirm the hypothesis that these values are highly linearly related an analysis will be conducted in which repeated measures correlation coefficient (rcmm) between BrAc and BAL will be obtained. In contrast to a simple correlation analysis of data in which repeated measures collected from individual subjects are used, here will be no violation of the assumption of independence of observations when rcmm values are utilized as the measure of the extent of correlation between these values [Bakdash and Marrusich, 2017].

Calibration Study of a Wearable Noninvasive Blood Alcohol Monitor
Final V1.8 4.24.19

Data obtained in the validation phase of this study will be analyzed using the proc glm procedure for SAS 9.4. This data will include values for individual subjects obtained for each time-point at which BrAc measurement were made and corresponding predicted BAL values determined for these subjects. This data will be analyzed using following general linear model:

BAL= BrAc sub

This model is equivalent to an analysis of covariance model in which subjects (sub) are a covariate. This model will allow for the determination of whether BrAc and BAL values are significantly related to one another. The correlation coefficient [rcmm] for relationship between BAL and BrAc will be determined using the following equation first mentioned by Bland and Altman [24] with sum of squares values being obtained from the results of our glm analysis: $rcmm = \text{square root} [\text{Sum of Squares BAL} / (\text{Sum of Squares BAL} + \text{Sum of Squares Residual})]$

Since both BrAc and BAL measurements are hypothesized to be linear, the rcmm value is expected to be >0.80 with high correlation power. The statistical null hypothesis is that the predicted BAL measurements are not related to the standard breathalyzer measurements. The study is designed to maintain a probability of Type I and Type II error rates with respect to the null hypothesis at $p<0.05$.

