12.2 Sample Size Determination

Calibration Study of a Wearable Noninvasive Blood Alcohol Monitor

Final V1.8 4.24.19

Power analysis: Eight concurrent readings of breathe (BAL) and transdermal alcohol concentration (TAC) will be obtained from the wristwatch sensor and the breathalyzer starting 15 minutes after the start of subject alcohol consumption to the end of the 60 minute drinking session. An additional 20 concurrent readings will be collected during the 5 hour observation period in phase I, and an additional 12 concurrent readings in the 3-hour observation period in phase II. This means that a possible 28 (Phase I) or 20 (phase II) points may be available for this analysis if only pairs of data are used for which values for both devices exceed zero. However, the sensitivity of the wristwatch sensor in human subjects is currently unknown, and so fewer than 20 data points may be of use for our analysis.

Data will be analyzed using a repeated measures correlation (rcmm) procedure described by Bland and Altman [24] and Bakdash and Marisich [25]. For the wristwatch device to be considered to be useful the r value for the correction between BrAc and predicted BAL measures must exceed 0.9. Cohen [26] defines a large effect size as being $r=0.5$. Bakdash and Marish provide power curves for the rcmm procedure. These curves indicate that for a large effect size ($r=0.5$) that the power approach 99% when data from only 10 points are available for sample size of about 7. We anticipate a repeated measures correlation value of at least 0.8 and hope to observe a correlation of 0.9. Bakdash and Marisich [25] indicate the degrees of freedom for determining rcm values can be determined using the following equation:

$$Df = (\text{Number of subjects}-2) \times (\text{number of data points} - 1).$$

The degrees of freedom can be used to determine the corresponding sample size, with the degrees of freedom for standard tables of power analysis being equal to $N-2$ ($Df=N-2$). Using this relationship we use the Proc Power procedure for Pearson correlations in SAS to determine the power for 21 data points collected for 9 subjects and 10 datapoints for 5 subjects. In both of these analyses the calculated power value was > 0.995 for rcm of 0.8 or 0.9.

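### The primary coefficient is computed from a sum of squares for BAL, but BAL is the response in the stated model, so formula and model together do not give the repeated measures correlation

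*Combined protocol and SAP*

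**What the plan says.** Section 4.2.1 makes the agreement between watch and breathalyzer in the second session the primary outcome: "BAL and wristwatch sensor data correlation will be analyzed by repeated measures correlation (rmcorr) analysis". Details are left to section 12.

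Section 12.1 (Validation Phase) first separates the two variables. BAL is the value derived from the watch ("TAC data collected during validation phase will be converted into predicted BAL values for individual subjects"), and BrAc is the breathalyzer reading. It then states a model with BAL on the left and BrAc and sub on the right, to be fitted in SAS proc glm, and adds: "This model is equivalent to an analysis of covariance model in which subjects (sub) are a covariate". The coefficient is defined as the square root of SS(BAL) / [SS(BAL) + SS(Residual)]. The term "Sum of Squares BAL" appears in both numerator and denominator, "with sum of squares values being obtained from the results of our glm analysis".

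Two benchmarks apply to the result. In section 12.1, "the rcmm value is expected to be >0.80". In section 12.2, for the device to count as useful, "the r value for the correction between BrAc and predicted BAL measures must exceed 0.9".

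**The concern.** A sum of squares for an effect belongs to a term on the right-hand side of the model. With BAL as the response, the analysis-of-variance table has rows for BrAc, sub and residual, and none for BAL. The plan therefore tells the analyst to read the primary coefficient from a row that does not exist. No other section gives a formula; sections 4.2.1 and 12.2 and the hypothesis table in 12.1 only name the procedure.

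The stated power exceeds 0.995 at a correlation of 0.8, so significance is close to assured there. The conclusion then rests on how large the coefficient is relative to 0.80 and 0.9, and its size is what the printed formula leaves open. An analyst who follows the text must pick a substitute, and the available substitutes disagree.

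**Working it through.** **Inputs from the plan.** Model, formula, and the 0.80 and 0.9 benchmarks: sections 12.1 and 12.2. Nine completers, up to 20 paired readings each in Phase II, and power above 0.995: section 12.2.

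**Input not in the plan.** The share *b* of BAL variance that lies between subjects. It is assumed to be 0, 0.25 or 0.5.

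**1. The plan's own power figure.** Section 12.2 uses Df = (subjects − 2) × (points − 1) and N = Df + 2.
- 9 subjects, 21 points: Df = 7 × 20 = 140, N = 142.
- 5 subjects, 10 points: Df = 3 × 9 = 27, N = 29.
- Pearson test, Fisher z with bias term, two-sided 0.05 (sidedness assumed): power 1.000 and 0.9999 at r = 0.8, and 1.000 for both at r = 0.9.

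The stated figure reproduces and does not depend on the formula at issue.

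**2. What the correct ratio gives.** Let SSW be the within-subject sum of squares of BAL and r the repeated measures correlation. Adjusted for subject, SS(BrAc) = r² × SSW and SS(Residual) = (1 − r²) × SSW. So SS(BrAc) / [SS(BrAc) + SS(Residual)] = r², and the root is |r|. The statistic is symmetric: with BrAc as response and BAL as predictor, the printed formula gives the same |r|.

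**3. What the other substitutes give.** With SST the corrected total, SSW = (1 − b) × SST and SS(Residual) = (1 − b)(1 − r²) × SST.
- SS(BAL) read as the model sum of squares (over model plus residual): √[1 − (1 − b)(1 − r²)].
- SS(BAL) read as the corrected total: 1 / √[1 + (1 − b)(1 − r²)].

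At r = 0.80, 1 − r² = 0.36, so (1 − b)(1 − r²) = 0.36, 0.27 and 0.18.

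| Reading of SS(BAL) | b = 0 | b = 0.25 | b = 0.5 |
|---|---|---|---|
| Subject-adjusted SS(BrAc), or sides swapped | 0.80 | 0.80 | 0.80 |
| Model SS | √0.64 = 0.800 | √0.73 = 0.854 | √0.82 = 0.906 |
| Corrected total SS | 1/√1.36 = 0.857 | 1/√1.27 = 0.887 | 1/√1.18 = 0.921 |
| True r at which 0.9 is reached, model SS | 0.900 | 0.864 | 0.787 |
| True r at which 0.9 is reached, total SS | 0.875 | 0.829 | 0.729 |

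At r = 0 the model reading gives √b = 0, 0.500 and 0.707. The total reading gives 0.707, 0.756 and 0.816, and can never fall below √0.5 = 0.707, because the residual cannot exceed the total.

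**4. Simulation at the trial's size** (9 subjects × 20 points, 2,000 runs per setting, r = 0.80; means for b = 0 / 0.25 / 0.5):
- subject-adjusted SS(BrAc): 0.799 / 0.798 / 0.799; swapped sides identical in every run (largest difference below 1e-15);
- model SS: 0.809 / 0.855 / 0.900;
- total SS: 0.863 / 0.888 / 0.917.

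**5. One simulated data set.** SS(BrAc) adjusted for subject = 94.44, SS(sub) entered first = 93.72, residual = 59.82, total = 247.98.
- Correct: √[94.44 / (94.44 + 59.82)] = 0.782.
- Swapped sides: 0.782.
- Total reading: √[247.98 / (247.98 + 59.82)] = 0.898.

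**6. Why replacing BAL by BrAc is not quite enough.** BrAc is listed before sub, so its Type I sum of squares is not adjusted for subject. If both measures have between-subject share b and subject means correlate ρ, the overall correlation is (1 − b)r + bρ. The coefficient becomes √{[(1 − b)r + bρ]² / ([(1 − b)r + bρ]² + (1 − b)(1 − r²))}. At r = 0.80, for ρ from 0 to 1:
- b = 0.25: √(0.36/0.63) = 0.756 to √(0.7225/0.9925) = 0.853;
- b = 0.5: √(0.16/0.34) = 0.686 to √(0.81/0.99) = 0.905.

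The square root also discards the sign, so −0.8 would be reported as 0.8.

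**The case against.** The strongest reply is that this is a labelling slip with an obvious reading. The plan names the repeated measures correlation and cites its method papers. Elsewhere it freely uses BAL for the breath reading, as in section 12.2: "Eight concurrent readings of breathe (BAL) and transdermal alcohol concentration (TAC". On that reading SS(BAL) is the breath predictor's sum of squares and, adjusted for subject, the formula is right. The ratio's shape, effect over effect plus residual, also argues against the total (which would count the residual twice) and against the model sum of squares (which would bring in subject differences). Calling the model an analysis of covariance points to the adjusted sum of squares.

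The inflation also depends on *b*. Every subject is dosed to the same 0.05 g/dL target, so a share as high as 0.5 has no support in the plan, although nothing excludes it. At b = 0 the model reading has no large-sample error. At b = 0.5 its large-sample 0.906 is 0.900 on average in simulation, at the 0.9 line and not clearly above it.

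Most of this stands, and it limits the weight of the point. It does not remove the mismatch: section 12.1 uses both names in the same model line, with BAL as the predicted value, so the looser usage elsewhere cannot settle which sum of squares is meant.

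**Conclusion.** The concern holds. The printed formula cannot be evaluated from the printed model, and no other section supplies a usable one. The intended statistic is not in doubt, and both likely repairs recover it exactly.

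The exposure is confined to the reported size of the primary coefficient. If an analyst substituted the model or total sum of squares, a true 0.80 would appear as 0.80 to 0.91 or 0.86 to 0.92, over the assumed range of *b* from 0 to 0.5. The plan proposes neither substitution, and the likelihood that an inflated value would be reported is low. The F test of BrAc adjusted for subject, the power and the sample size are unaffected. Because this coefficient is the primary outcome and is judged against numerical thresholds, the text should be corrected before the validation data are analysed.

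**What to change.** In section 12.1, replace the model and formula with:

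- CLASS sub; MODEL BAL = sub BrAc;
- rcmm = sign(BrAc slope) × √[Type III SS(BrAc) / (Type III SS(BrAc) + SS(Residual))].

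Name the Type III (subject-adjusted) sum of squares explicitly, so that the result does not depend on the order of terms. In the sentence on analysis of covariance, describe sub as the class factor and BrAc as the covariate; the current text gives the covariate role to subject.

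The cost is a few words in one section. No data collection, sample size or power calculation changes.

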Given that BAL and BrAc are expected to be equivalent it is also hypothesized that there will be a strong correlation between Cmax and Tmax values. Pearson correlation coefficients for correlation analysis between both Cmax and Tmax determined from individual subjects' BrAc and BAL curves, therefore, are expected to be 0.8 or greater, with p values being less than 0.05.

Hypothesis	Planned Analyses
1. There will be a significant correlation between BrAc predicted BAL measures	Repeated measures correlation analysis of wristwatch TAC measurements and contemporaneous BAC measurements from breathalyzer.
2. There will be a significant correlation between Cmax and Tmax values obtained for paired BrAc and predicted BAL measurements.	Pearson correlation analysis for Tmax and Cmax values obtained for BrAc and predicted BAL data.

We expect that the results of this study will demonstrate the effectiveness of the developmental wristwatch transdermal alcohol sensor. Furthermore, these results and the developmental work to calibrate this wristwatch will contribute significant knowledge toward the understanding of reliable measurement of blood alcohol via transdermal routes.

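### The primary correlation has two unlinked decision marks: significance against zero in 12.1 and r above 0.9 for usefulness in 12.2

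*Combined protocol and SAP*

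**What the plan says.** Section 4.2.1 defines the endpoint and refers to section 12 for its analysis: "The primary outcome is the correlation in estimated BAL as measured by the breathalyzer and the wristwatch sensor during the second alcohol self-administration trial".

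Section 12.1 supplies the test. "The statistical null hypothesis is that the predicted BAL measurements are not related to the standard breathalyzer measurements", with both error rates set at 5%. The hypothesis table gives the matching claim: "There will be a significant correlation between BrAc predicted BAL measures". It names no size of correlation. The text of 12.1 adds that "the rcmm value is expected to be >0.80 with high correlation power". After the table, 12.1 says that the results are expected to show that the sensor is effective.

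Section 12.2 introduces a different mark. For the device to be considered useful, "the r value for the correction between BrAc and predicted BAL measures must exceed 0.9" (in context, a correlation). A few sentences later it reads: "We anticipate a repeated measures correlation value of at least 0.8 and hope to observe a correlation of 0.9". It then reports power above 0.995 at r = 0.8 or 0.9, for "21 data points collected for 9 subjects and 10 datapoints for 5 subjects".

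The 0.9 bar does not appear in 4.2.1, in 12.1 or in the hypothesis table.

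**The concern.** Section 4.1 asks whether the sensor is sensitive and reliable against the breathalyzer. Rejecting a correlation of zero is weak evidence on that question, because both curves rise and fall after a single dose. The mark that speaks to adequacy is 0.9. It stands only in the sample size section, is not tied to the hypothesis, and is softened to a hope within the same paragraph. Nor does the plan say whether the point estimate or a confidence limit has to clear it.

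At stake is the headline conclusion. A moderate but significant correlation would confirm Hypothesis 1, and 12.1 would not prevent its being presented as a demonstration of effectiveness, although 12.2 would class the device as not useful. The high stated power could also be misread as a high chance of clearing the bar.

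**Working it through.** **Inputs.** From 12.2: scenarios of 9 subjects x 21 points and 5 x 10; up to 20 points per subject in Phase II; Df = (subjects - 2) x (points - 1); N = Df + 2; anticipated r of at least 0.8; usefulness bar 0.9. From 12.1: null of no relation, 5% level. Assumed: two-sided test (sidedness is not stated) and independent readings.

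**1. Reproduce the stated power.** Df = 7 x 20 = 140, so N = 142; Df = 3 x 9 = 27, so N = 29. Fisher z power against zero is Phi(atanh(r) x sqrt(N - 3) - 1.96).
- N = 29, r = 0.8: 1.0986 x 5.099 - 1.96 = 3.64, power 0.9999 (0.9998 by simulating the t-test).
- N = 142, r = 0.8: 1.0986 x 11.790 - 1.96 = 10.99, power above 0.9999.
- At r = 0.9, power is above 0.9999 in both cases.

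The figure of more than 0.995 is correct, for a null of zero.

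**2. Smallest observed r that meets Hypothesis 1.** r = t / sqrt(Df + t²), with t the two-sided 5% point.

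| Scenario | Df | Critical r |
|---|---|---|
| 9 x 21, plan's formula | 140 | 0.165 |
| 9 x 20, plan's formula | 133 | 0.169 |
| 9 x 20, Df implied by the 12.1 model, 9 x 19 - 1 | 170 | 0.150 |
| 5 x 10, plan's formula | 27 | 0.367 |

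Every estimate from these values up to 0.9 confirms Hypothesis 1 and misses the usefulness bar.

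**3. Chance that the estimate exceeds 0.9.** 1 - Phi((atanh(0.9) - atanh(true r)) x sqrt(N - 3)), with atanh(0.9) = 1.4722.

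| True r | N = 142 | N = 29 |
|---|---|---|
| 0.80 | about 0 | 0.03 |
| 0.85 | 0.005 | 0.14 |
| 0.90 | 0.50 | 0.50 |
| 0.95 | 1.00 | 0.97 |

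Example, true r = 0.8 and N = 29: (1.4722 - 1.0986) x 5.099 = 1.905, giving 0.028.

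**4. If the bar applies to the lower limit of a two-sided 95% interval.** The observed r must exceed tanh(1.4722 + 1.96 / sqrt(N - 3)). That is 0.927 for N = 142 and 0.952 for N = 29. The estimate-or-limit choice is therefore not cosmetic.

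**The case against.** The best defence is that the two marks answer different questions. The test in 12.1 asks whether the measures are associated; the 0.9 bar asks whether the association is close enough for use. An r of 0.85 then reads coherently as related but short of useful. The bar is also prespecified, in the statistical section, shortly after the hypothesis table. Much of this stands: the two conclusions need not contradict each other, and a sponsor who reads 12.2 could not call such a device useful. What remains is that the plan never draws this distinction, does not rank the marks, and is not firm about 0.9 within 12.2.

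Two stronger readings are tempting. A reader might infer three competing success marks, counting 0.80 as one. The documents do not support that: 0.80 is worded throughout as expected or anticipated, and no decision hangs on it. A reader might also infer that a result between 0.80 and 0.90 is near certain. With a true r of 0.85, the chance is indeed 96 to 98% with nine completers, but it is 65% in the plan's 5 x 10 case, and 0.85 is a value that the documents never state.

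**Conclusion.** The point holds in limited form. There are two decision marks for one endpoint, neither linked nor ranked, and the plan allows the primary hypothesis to be confirmed for a device that misses the plan's own bar for usefulness. The gap between the marks is wide: from roughly 0.15 to 0.37, depending on usable data, up to 0.9. If the sponsor's anticipated 0.8 is the truth, the device will almost surely miss the bar; even at a true 0.9 the odds are even.

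These chances rest on independent readings, and 15-minute readings on one curve are unlikely to be independent. Dependence would widen the spread of the estimate, so the 0 to 3% could be somewhat higher; the even odds at a true 0.9 would change little. The conflict in wording depends on none of this. The primary estimate can still be computed, so this should be corrected but does not invalidate the study.

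**What to change.** Before Phase II data are seen:

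- In 12.1 and the hypothesis table, label the p<0.05 test as showing that an association was detected, and no more.
- In the same places, carry over the 12.2 bar (rcmm above 0.9) as the criterion for concluding that the device is useful. State whether it applies to the point estimate or to the lower confidence limit, and at what level.
- In 12.2, reconcile the requirement for 0.9 with the later hope of observing it. If 0.9 is not meant to bind, say so and name the criterion that does.
- Label 0.80 as a planning expectation.
- State that the power above 0.995 refers to zero correlation, and set beside it the chance of clearing 0.9.

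The cost is a few lines of text and a short calculation, with no added subjects, visits or measurements. The downside for the sponsor is that significance alone can no longer be reported as success, and the power statement will look less favourable.

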12.2 Sample Size Determination

Calibration Study of a Wearable Noninvasive Blood Alcohol Monitor

Final V1.8 4.24.19

Power analysis: Eight concurrent readings of breathe (BAL) and transdermal alcohol concentration (TAC) will be obtained from the wristwatch sensor and the breathalyzer starting 15 minutes after the start of subject alcohol consumption to the end of the 60 minute drinking session. An additional 20 concurrent readings will be collected during the 5 hour observation period in phase I, and an additional 12 concurrent readings in the 3-hour observation period in phase II. This means that a possible 28 (Phase I) or 20 (phase II) points may be available for this analysis if only pairs of data are used for which values for both devices exceed zero. However, the sensitivity of the wristwatch sensor in human subjects is currently unknown, and so fewer than 20 data points may be of use for our analysis.

Data will be analyzed using a repeated measures correlation (rcmm) procedure described by Bland and Altman [24] and Bakdash and Marisich [25]. For the wristwatch device to be considered to be useful the r value for the correction between BrAc and predicted BAL measures must exceed 0.9. Cohen [26] defines a large effect size as being $r=0.5$. Bakdash and Marish provide power curves for the rcmm procedure. These curves indicate that for a large effect size ($r=0.5$) that the power approach 99% when data from only 10 points are available for sample size of about 7. We anticipate a repeated measures correlation value of at least 0.8 and hope to observe a correlation of 0.9. Bakdash and Marisich [25] indicate the degrees of freedom for determining rcm values can be determined using the following equation:

$$Df = (\text{Number of subjects}-2) \times (\text{number of data points} - 1).$$

The degrees of freedom can be used to determine the corresponding sample size, with the degrees of freedom for standard tables of power analysis being equal to $N-2$ ($Df=N-2$). Using this relationship we use the Proc Power procedure for Pearson correlations in SAS to determine the power for 21 data points collected for 9 subjects and 10 datapoints for 5 subjects. In both of these analyses the calculated power value was > 0.995 for rcm of 0.8 or 0.9.

If the existence of a time lag is found that precludes the usefulness of rcm values then Pearson correlations will be determined for AUC and Cmax values. For both of these value obtained for the TAC-BAL data for $r=0.8$, power will equal 0.82 for a sample size of 9 subjects who complete Phase I and Phase II. We anticipate consenting 36 subjects to achieve a sample size 12 randomizers and 9 completers.

Given that this is a laboratory-based experiment we do not plan to conduct any planned interim analyses in this study.

13 Ethics/Protection of Human Subjects

This study is to be conducted according to applicable US federal regulations and institutional policies (which are based in federal regulations, guidance, and ICH Good Clinical Practice guidelines).

This protocol and any amendments will be submitted to the Boston Medical Center and Boston University Medical Campus IRB, for formal approval of the study conduct. The decision of the

Calibration Study of a Wearable Noninvasive Blood Alcohol Monitor

Final V1.8 4.24.19

IRB concerning the conduct of the study will be made in writing to the investigator. A copy of the initial IRB approval letter will be provided to the sponsor before commencement of this study.

All subjects for this study will be provided a consent form describing this study and providing sufficient information for subjects to make an informed decision about their participation in this study. The consent form will be submitted with the protocol for review and approval by the IRB. The consent of a subject, using the IRB-approved consent form, must be obtained before that subject is submitted to any study procedure. Consent will be documented as required by the IRB.

14 References

1. Pantelopoulos, A. and N.G. Bourbakis, A survey on wearable sensor-based systems for health monitoring and prognosis. *IEEE Transactions on Systems, Man and Cybernetics, Part C (Applications and Reviews)*, 2010. 40(1): p. 1-12.
2. Allet, L., et al., Wearable Systems for Monitoring Mobility-Related Activities in Chronic Disease: A Systematic Review. *Sensors*, 2010. 10(10): p. 9026-9052.
3. Patel, S., et al., A review of wearable sensors and systems with application in rehabilitation. *Journal of Neuroengineering and Rehabilitation*, 2012. 9: p. 17.
4. Y. Hao, R. Foster, "Wireless Body Sensor Networks for Health Monitoring Applications," *Physiol. Meas.*, 29, R27-R56 (2008).

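### The pairs that give the primary repeated measures correlation are not consistently defined between 12.1 and 12.2, and the reading counts and degrees-of-freedom formula in 12.2 need correcting

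*Combined protocol and SAP*

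**What the plan says.** - **Analysis data (12.1).** For the primary model: "This data will include values for individual subjects obtained for each time-point at which BrAc measurement were made", with the matching predicted BAL. No exclusion of zeros is stated. On size: "the rcmm value is expected to be >0.80 with high correlation power".
- **Zero-BAL hour (Section 9).** Breath readings are taken every 15 minutes for 60 minutes before drinking, to check the watch for false positives. The Phase II validation session repeats the same four stages.
- **Reading counts (12.2).** "Eight concurrent readings of breathe (BAL) and transdermal alcohol concentration (TAC) will be obtained from the wristwatch sensor and the breathalyzer" between 15 minutes after the start of drinking and the end of the 60-minute session. Observation adds 20 in Phase I and 12 in Phase II. Hence "a possible 28 (Phase I) or 20 (phase II) points may be available for this analysis if only pairs of data are used" with both values above zero. The section adds that "the sensitivity of the wristwatch sensor in human subjects is currently unknown, and so fewer than 20 data points may be of use".
- **Usefulness figure (12.2).** "the r value for the correction between BrAc and predicted BAL measures must exceed 0.9".
- **Power (12.2).** For r = 0.5, published curves are cited as showing that "the power approach 99% when data from only 10 points are available for sample size of about 7". It then says "the degrees of freedom for determining rcm values can be determined using the following equation": (subjects − 2) × (points − 1). Power above 0.995 is reported at r = 0.8 or 0.9, for 21 points on 9 subjects and for 10 points on 5 subjects.

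**The concern.** Two choices are open: whether the zero-BAL hour enters the primary r, and whether a pair is dropped when a device reads zero after drinking has begun.

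Both matter for a within-subject correlation. A clean stretch of zeros on both devices lengthens the range and raises r; a false signal during that hour can lower it. Dropping pairs because the watch reads zero lets the device's own misses select the data by which it is judged, and that can also move r either way.

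If the set is not fixed before Phase II data are seen, whether r is reported as above or below 0.9 (or the expected 0.80) can depend on a later choice. Separately, the counts and df in 12.2 do not follow from the schedule or from the model in 12.1.

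**Working it through.** **1. The plan's power figure.** Fisher z power against zero correlation, two-sided 0.05 (sidedness is not stated, so assumed), n = df + 2.

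- 9 subjects × 21 points: (9 − 2)(21 − 1) = 140 df; power at r = 0.8 is above 0.999.
- 5 subjects × 10 points: (5 − 2)(10 − 1) = 27 df; power 0.9999.

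The stated power above 0.995 reproduces.

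**2. Reading counts.** At 15-minute spacing, the window from 15 to 60 minutes holds readings at 15, 30, 45 and 60: 4, not 8. Phase I: 4 + 20 = 24, not 28. Phase II: 4 + 12 = 16, not 20. The 21 used for power matches neither stated total.

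**3. Degrees of freedom.** The 12.1 model has one mean per subject and one common slope. With N subjects and k pairs each, residual df = Nk − 1 − (N − 1) − 1 = N(k − 1) − 1.

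| N × k | 12.2 formula | 12.1 model |
|---|---|---|
| 9 × 21 | 140 | 179 |
| 9 × 16 | 105 | 134 |
| 5 × 10 | 27 | 44 |
| 7 × 10 | 45 | 62 |

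At r = 0.8 the first three rows give power above 0.999 under either formula. For the cited 7 × 10 case at r = 0.5, 45 df gives 0.954 and 62 df gives 0.990; the latter agrees better with the cited 99%.

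**4. Effect of the pair set.** The documents give no watch error, residual lag or detection limit, so every input here is assumed: 9 subjects; peak 0.05 g/dL (SD 0.007) at 60–80 minutes; linear elimination 0.015 g/dL per hour (SD 0.002); breath error SD 0.002. Lag means what remains after the Phase I correction. Mean pooled within-subject r, clean baseline:

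| Watch SD | Lag | 16 post-start pairs | 20 pairs, zero-BAL hour added |
|---|---|---|---|
| 0.004 | none | 0.95 | 0.97 |
| 0.004 | 10 min | 0.90 | 0.94 |
| 0.004 | 15 min | 0.85 | 0.91 |
| 0.004 | 20 min | 0.78 | 0.87 |
| 0.010 | none | 0.79 | 0.86 |

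At a 15-minute lag, r exceeds 0.9 in 0% of simulated trials without the zero-BAL hour and about 90% with it.

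The reverse direction, with SD 0.004 and a start-up false signal of mean 0.03 g/dL decaying over 40 minutes: adding the hour takes r from 0.92 to 0.88 at a 10-minute lag. With a mean of 0.02 there is almost no change (0.913 to 0.917).

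Dropping zeros, post-start readings:

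- 10% of watch readings falsely zero, SD 0.003, no lag: 0.76 with zeros kept, 0.96 on both-above-zero pairs.
- Detection limit 0.02 with a 15-minute lag: r falls from 0.82 to 0.74 when zeros are dropped.

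**The case against.** - **The two sections do not prescribe rival rules.** A reader might infer a flat contradiction. That goes too far: the both-above-zero wording in 12.2 is a condition inside a sample-size paragraph. The sentence in 12.1 is the only description of the analysis data. What stands is that 12.2 counts a different set and leaves the usable number to unknown watch sensitivity.
- **Other sections lean towards leaving the zero-BAL hour out.** Section 4.2.1 refers to the second self-administration trial, Section 5 to the drinking and observation periods, and Section 9 gives the hour its own purpose and starts the drinking session after it. This is a fair reading, but the synopsis uses the word trial for a whole visit, and none of these places deals with zeros.
- **0.9 is not the formal test.** A reader might infer that the primary hypothesis could pass or fail on the pair set. It could not in any material way: the null is no relation, and 12.2 only hopes for 0.9. The stake is whether the watch is called useful.
- **The crossings depend on chosen inputs.** This stands. At SD 0.004 with no lag, r passes 0.9 on both sets; at a 20-minute lag it fails on both. The false signal that lowers r has a mean of 60% of the target peak (0.03/0.05) and would show in the false-positive check. With a large lag, 12.2 may move to AUC and Cmax, though it gives no threshold.
- **The extra readings may be zero-BAL readings.** Four of them plus 16 make 20, or 21 counting both ends of the grid. But 12.2 starts its count after drinking begins and requires values above zero, so its wording does not allow this.
- **The cited 99% is approximate.** It is given for about 7 subjects, so it supports the df correction but does not prove it. The model derivation is enough.

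**Conclusion.** The concern holds as an under-specified analysis set and should be fixed; it does not invalidate the design. Under assumed sensor behaviour, the zero-BAL hour or the handling of zeros can move r across 0.9 in either direction; at low or high error neither changes the reading. How likely a crossing is cannot be said, because the documents give no sensor performance in humans.

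The count of 8, the totals of 28 and 20, the 21 used for power and the df formula are wrong or unreconciled as written, but minor. A reader might infer that the study is underpowered. It is not, for the test planned: the 12.2 formula understates df, and at 9 × 16 the power at r = 0.8 remains above 0.995. N = 9 is unaffected. That power is against zero correlation and says nothing about exceeding 0.9.

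**What to change.** Before Phase II data are seen:

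1. State one primary pair set in both 12.1 and 12.2: all scheduled pairs from 15 minutes after the start of drinking to the end of the planned 3-hour observation, keeping zero readings from either device. Say whether readings from a stay extended beyond 3 hours, which Section 9 allows, are excluded. Keeping zeros is a recommendation, so that device misses do not select the data.
2. Report the zero-BAL hour separately as the false-positive check of Section 9. Give r with that hour included, and r on both-above-zero pairs, as labelled sensitivity results.
3. Reconcile 8, 28, 20 and 21 with the 15-minute schedule (4, 24 and 16 after the start of drinking).
4. Use df = total pairs − N − 1, which is N(k − 1) − 1 when every subject has k pairs, and restate power at 9 × 16 (df 134, above 0.995 at r = 0.8).

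The cost is a few lines of text, with no change to sample size, visits or procedures. The downside is that r may be lower than under a more favourable set.
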